### IV. SUBJECT ENROLLMENT

Randomization and Enrollment: This study will utilize a matched-pair cluster randomized design with the intervention on the cluster level, and the main outcome (6 month minus baseline change in SBP) measured at the patient level. We will have 174 clusters (made up of 185 clinicians) in the study. We will match pairs of clusters with similar number of patients and prior year mean blood pressure of patients in the cluster. One cluster in each pair will be randomized to the intervention and unit one to usual care. Patients will be electronically identified and included in the study over the course of 12 months. Patients seen by PCPs during the pilot study will be excluded. Retrospective data indicates that 70% of patients have a follow-up around 6 months. Outcomes assessment will occur at 180 days (+/- 60 days). After the 12-month enrollment period ends, data collection will continue for 6 months so that those enrolled toward the end of the enrollment period will have a full 6 months to complete any interventions ordered by the PCP. A small subset of PCPs will be enrolled in a pilot study for approximately one month, as described below in study procedures Aim 1b. Clinical outcomes will be recorded and reviewed every month over the course of the trial.

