## V. STUDY PROCEDURES

### **Aim 1, and 1a Study Procedures:**

Modify Rules for Automated Diagnosis of CKD and Uncontrolled HTN: [name] is a participant in the NKDEP Health Information Technology care plan working group. She has contributed to their efforts to new national standards for diagnosis of patients with CKD using EHR data. We will modify the rules from the MAPLE study in order to align them with this new national standard. Then, we will create rules for automated diagnosis of uncontrolled hypertension. We will implement the BPA in “silent mode” for the control arm. This means that we will identify control patients in real time according to the same inclusion criteria as intervention patients, excluding all patients who are pregnant.

Develop Rules for Evidence-based Recommendations for HTN in CKD: We will leverage past work that we have done in a study that delivered recommendations based on JNC7. An example of one of the rules is to determine whether anti-hypertensive agents have been prescribed but are not at highest potency. If so, the CDS will deliver a recommendation to increase the dosage. Or, if multiple agents have been prescribed at maximum potency, the CDS will access the patient’s refill record. If the patient has not been refilling medications on schedule, the tool will recommend a medication adherence discussion. We will also include one-click access to documentation and orders relevant for CKD. For example, a message that gives a specific diagnosis, “This patient has stage 3b CKD with unknown level of albuminuria”), as well as an actionable order, “Click here to order a urine microalbumin to creatinine ratio test.” The BPA will include a BP entry field in which a PCP can record a repeat BP reading. If the PCP enters a BP reading, it will automatically be recorded in the vital signs flowsheet and vice versa. We will include appropriate laboratory monitoring test orders. Confirmatory testing is appropriate for an abnormal urine albumin level, so we will include an order if the prior result was abnormal. We will also provide one-click access to print patient handouts. In order to minimize cognitive overload and improve self-efficacy we will only deliver three messages at one time. We will develop a ranked list to drive the choice of recommendations. For example, in patients with CKD and HTN who smoke, tobacco cessation would be the highest priority.

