Implementation of CDS in Epic: The next step is implementation in Epic as a BPA. Each of the rules will be added to the Epic database. The BPAs appear in an area of the screen that is visible when orders are being entered. Currently, there are several cancer screening BPAs and a seasonal influenza BPA. The CDS will be moved to the Production environment in “silent mode” before the scheduled start date of the trial, where it will record when it would fire, but it will not be displayed to the user. This step will allow us to validate that the rules are accurately identifying patients and producing the correct recommendations through a chart review. We will review 10 charts of patients with CKD and uncontrolled HTN per clinic for a total of 150 charts. The CDS will be activated in the Production environment on the start date of the clinical trial in Aim 2.

Validation of Hypertension-specific Process Measures: In preparation for the clinical trial in Aim 2, we will validate three process measures. Two of the measures will reflect treatment intensification by the PCP, 1) an increase in dosage or 2) addition of a new anti-hypertensive agent. The third measure will reflect medication adherence by the patient using data from a pharmacy benefits manager. We will perform a retrospective chart review of 150 charts to calculate the sensitivity and specificity of each rule.

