## VI. BIOSTATISTICAL ANALYSIS

Data collected during the pilot study will not be included in the final analysis. Patients enrolled in the pilot study will not be enrolled in the final analysis. However, PCPs in the pilot study will be included in the intervention arm of the main clinical trial. A subgroup analysis will be performed on patients of these PCPs.

Table 1. Outcome Variables and Measures for Both Arms

Measurement Variable	Form of Variable	Analysis Metric	Time Point
Primary			
Mean SBP	Continuous	Change from baseline	6 months, 12 months, 18 months
Secondary			
Controlled SBP Rate	Dichotomous	Proportion of patients with controlled SBP rate	6 months, 12 months, 18 months
Urine Albumin to Creatinine Ratio	Continuous	Urine Albumin to Creatinine Ratio	6 months, 12 months, 18 months
Serum Creatinine > 2.0	Dichotomous	Proportion of patients with Creatinine > 2.0	Monthly
eGFR	Continuous	eGFR	6 months, 12 months, 18 months

Medication ordered	Dichotomous	Proportion of patients with recommended medication ordered	6 months
Basic metabolic panel ordered	Dichotomous	Proportion of patients with basic metabolic panel ordered	6 months
Referral to e-consults	Dichotomous	Proportion of patients with referral to e-consults	6 months
BPA acceptance	Dichotomous	Proportion of patients where BPA was accepted	6 months
Mean SBP of less than 110	Dichotomous	Proportion of patients with mean SBP of less than 110	Monthly
Newly documented allergy	Dichotomous	Proportion of patients with newly documented allergy due to adverse drug events	Monthly
K+ > 5.2	Dichotomous	Proportion of patients with K+ > 5.2	Monthly
K+ < 3.6	Dichotomous	Proportion of patients with K+ < 3.6	Monthly
Mean SBP intent-to-intervene analysis with imputation of missing 6-month BP measurement	Dichotomous	Proportion of patients with missing 6-month BP measurement	6 months
Controlled SBP Rate intent-to-intervene analysis with imputation of missing 6-month BP measurement	Dichotomous	Proportion of patients with missing 6-month BP measurement	6 months

Table 2. Outcome Variables and Measures for Intervention Arm Only

Measurement Variable	Form of Variable	Analysis Metric	Time Point
Acknowledgment reason entered	Dichotomous	Proportion of patients with acknowledgment reason entered	6 months
Feedback button clicked	Dichotomous	Proportion of patients with feedback button clicked	6 months

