## IX. MONITORING AND QUALITY ASSURANCE

The investigators will establish an independent Data Safety Monitoring Board (DSMB), which will serve as an independent group to monitor participant safety, study burden and scientific validity of the clinical data. The PI will ensure that the research is conducted in an ethical manner in accordance with good clinical practice and meets all applicable regulatory laws and policies. In addition to meeting the responsibilities for protecting the rights, safety, and welfare of the subjects enrolled in the research, the PI will review safety data, study conduct, procedural safety enrollment, adverse events, and other study-related information. The PI and co-investigators will review enrollment, adverse events and any recent literature that may be relevant to the research on a quarterly basis. Formal minutes with discussion points and remediation/actions plans (e.g. changes to protocol and consent documents) will be created, maintained, and relayed to the DSMB. The DSMB will convene in person or by teleconference once per year. At this meeting, the board will review any cases where systolic blood pressure was found to be below 110 mmHg, any reported adverse events, and deaths of enrolled patients.

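### Table 1's new-allergy row is not limited to drugs the decision support promotes, so unrelated entries dilute the one row that records drug intolerance

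*Combined protocol and SAP*

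**What the plan says.** Section VI (Biostatistical Analysis), Table 1, lists newly documented allergy as a dichotomous secondary outcome for both arms, assessed monthly. Its metric is "Proportion of patients with newly documented allergy due to adverse drug events". No drug, drug class or start date is given, and no other section supplies one.

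The other Table 1 rows that track harm from treatment are thresholds, also monthly: "Proportion of patients with mean SBP of less than 110", "Proportion of patients with Creatinine > 2.0", "Proportion of patients with K+ > 5.2", and a matching row for K+ below 3.6.

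The intervention's drug advice is described in section V (Study Procedures, Aim 1 and 1a). One rule, offered as an example, is to "determine whether anti-hypertensive agents have been prescribed but are not at highest potency" and, if so, to recommend a higher dose. In the same section, the validation of hypertension-specific process measures names the class, as in "addition of a new anti-hypertensive agent".

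Outside Table 1, section IX (Monitoring and Quality Assurance) has the data safety monitoring board meet once a year to review cases of low systolic pressure together with "any reported adverse events, and deaths of enrolled patients".

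**The concern.** The treatment-intensification measures are tied to antihypertensive drugs, but the row that would show patients reacting to those drugs is tied to no drug at all. A new entry for an antibiotic or an analgesic scores the same as one for a drug that the CDS prompted. Such entries should arise at about the same rate in both arms, so they add events without adding to the contrast.

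The threshold rows do not fill this gap. They capture low pressure, raised creatinine and abnormal potassium, but they do not record that a patient reacted to a drug or could not tolerate it. The yearly board review of adverse events is not described as a comparison between arms. If the trial leads clinicians to start or increase drugs that some patients cannot tolerate, the allergy row is where Table 1 would show it. What is at stake is how clearly that row can show a real excess.

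**Working it through.** **Stated figure.** There is none to reproduce. The documents give no expected rate, effect size, alpha, power or intracluster correlation (ICC) for this row.

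**Inputs from the documents**
- 2,350 patients (section II, Specific Aim 2a).
- Clusters: "We will have 174 clusters (made up of 185 clinicians) in the study" (section IV), paired, with one of each pair allocated to each arm. This gives about 2,350 / 2 = 1,175 patients per arm and a mean cluster size of 2,350 / 174 = 13.5.

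**Assumed inputs**
- Entries for drugs the CDS can recommend: 1% in control, 2% in intervention.
- Background of unrelated entries: 0 to 5 points, equal in both arms.
- Two-sided 5% test; no clustering at first.

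**Formula.** Power = Φ[(d − 1.96·se0) / se1], where d = p1 − p0, p̄ = (p0 + p1)/2, se0 = √[p̄(1 − p̄)·2/n] and se1 = √{[p0(1 − p0) + p1(1 − p1)]/n}.

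**Restricted outcome, 1% v 2%.** se0 = √(0.015 × 0.985 × 2/1,175) = 0.00502 and se1 = √[(0.0099 + 0.0196)/1,175] = 0.00501. Then (0.01 − 0.00983)/0.00501 = 0.03, so power is 51%.

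**One point of background added, 2% v 3%.** se0 = √(0.025 × 0.975 × 2/1,175) = 0.00644 and se1 = 0.00644. Then (0.01 − 0.01262)/0.00644 = −0.41, so power is 34%.

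| Background (points) | Observed rates | Risk ratio | Power |
|---|---|---|---|
| 0 | 1% v 2% | 2.00 | 51% |
| 1 | 2% v 3% | 1.50 | 34% |
| 2 | 3% v 4% | 1.33 | 26% |
| 3 | 4% v 5% | 1.25 | 21% |
| 5 | 6% v 7% | 1.17 | 16% |

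**A larger effect, with overlap allowed.** Some patients may have both kinds of entry. Let a be the rate for promoted drugs and b the background, taken as independent, so that the observed rate is 1 − (1 − a)(1 − b). With a = 2% v 4%:
- b = 0: risk ratio 2.00, difference 2.00 points, power 81%.
- b = 4%: rates 5.92% v 7.84%, risk ratio 1.32, difference 1.92 points, power 45%.

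The absolute difference hardly moves. The risk ratio and the power do.

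**Clustering.** With an assumed ICC of 0.05, the design effect is 1 + (13.5 − 1) × 0.05 = 1.63, leaving about 723 effective patients per arm. For 2% v 4%, power is 61% restricted and 30% with a 4% background. For 1% v 2%, it is 35% restricted and 23% with a 1% background.

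The direction is the same in every case. The size depends on rates the documents do not give.

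**The case against.** Several counter-arguments have force.

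- **The any-drug reading comes from silence.** The row is one line and never says that every drug counts. This stands as a caveat: the team may intend a narrower rule. But nothing in the text narrows it, and writing the rule down is still the remedy.
- **Antihypertensives may not be the only route to harm.** The potency rule is only an example. Section II describes the CDS scope as CKD and hypertension management, and section V gives tobacco cessation top priority for smokers. No full list of recommended drugs is given. So a reader should not infer that every entry outside the antihypertensive classes is pure noise, and a restriction to that class alone could miss reactions. This stands and shapes the fix.
- **It is not the only harm outcome.** A reader might take this row to be the trial's whole evidence on drug harm. It is not. Section VII names hypotension and an acute fall in kidney function as the overtreatment risks, and the SBP and creatinine rows address those. Only the narrower statement about intolerance holds.
- **Nothing says the row will be tested.** A reader might infer that the plan builds in a falsely reassuring null. The documents set no test or power for this row and do not use a null on it to declare safety. Broad capture is also reasonable for monthly monitoring.
- **Power is modest even after restriction.** At 1% v 2% it is 51% before clustering. Few events, as well as the definition, limit sensitivity.

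These points reduce the weight of the concern. They do not remove the dilution, and broad capture can be kept alongside a focused comparison.

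**Conclusion.** The point holds as a minor one. As written, the allergy row counts new entries for drugs unrelated to the intervention in both arms, and it is the only Table 1 row that records drug intolerance. Balanced background leaves the absolute difference nearly intact, shrinks the risk ratio and lowers sensitivity. In the main illustration, power falls from 51% to between 34% and 16%.

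Those figures rest on assumed event and background rates, a two-sided 5% test, an even split of 2,350 patients and no clustering. They show direction and plausible scale, and they are not a forecast. The documents do not support saying that the plan leaves drug harm unmeasured or makes a null on this row likely by design. The primary SBP comparison is not affected.

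**What to change.** Define the between-arm outcome as a new allergy or intolerance entry, dated after enrolment, for any drug class the CDS can recommend: the antihypertensives and any other class on its rule list. Keep the any-drug count as a descriptive safety row, so that unexpected reactions stay visible. Report the absolute difference with its confidence interval beside the risk ratio, since the former is little affected by background.

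The cost is small. The class list must be taken from the CDS rules and fixed before outcomes are compared by arm. The EHR allergy entry must also identify the causative drug and carry a date. The documents do not confirm either, so this should be checked first. Treatment and enrolment are unchanged.

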## VII. RISKS AND DISCOMFORTS

There are minimal risks to physicians or patients as a result of the intervention. For clinicians, there is a risk that the decision support and other tools could have unexpected adverse consequences such as creation of more work, unfavorable workflow issues, and overdependence on technology. Although important to consider, these risks are balanced by evidence suggesting the effectiveness of computerized clinical decision support to improve the quality of patient care. For patients, the risks are those that are typically undertaken in the receipt of general medical care. That is, it is conceivable that the intervention could result in a change in management (e.g., ordering more tests, referral), but in the case of chronic kidney disease this may in fact lead to a clinical benefit. There also is the possibility of psychological risk to patients associated with being labeled as having chronic kidney disease; however, this risk is outweighed by the potential benefits associated with better evaluation and treatment of the disease. Finally, there is a risk of overtreatment of hypertension which may cause hypotension or an acute decrease in kidney function. The intervention is delivered to the primary care physician, who will weigh the risk and benefit of treatment intensification. However, this risk is expected to be low since we only recommend treatment intensification within consensus guidelines.

## VIII. POTENTIAL BENEFITS

This research has the potential benefit of improving the quality of care for patients in the intervention practices, which ultimately could prevent disease progression and death. There are no potential benefits to the control subjects, who will receive current standard of care.

## IX. MONITORING AND QUALITY ASSURANCE

The investigators will establish an independent Data Safety Monitoring Board (DSMB), which will serve as an independent group to monitor participant safety, study burden and scientific validity of the clinical data. The PI will ensure that the research is conducted in an ethical manner in accordance with good clinical practice and meets all applicable regulatory laws and policies. In addition to meeting the responsibilities for protecting the rights, safety, and welfare of the subjects enrolled in the research, the PI will review safety data, study conduct, procedural safety enrollment, adverse events, and other study-related information. The PI and co-investigators will review enrollment, adverse events and any recent literature that may be relevant to the research on a quarterly basis. Formal minutes with discussion points and remediation/actions plans (e.g. changes to protocol and consent documents) will be created, maintained, and relayed to the DSMB. The DSMB will convene in person or by teleconference once per year. At this meeting, the board will review any cases where systolic blood pressure was found to be below 110 mmHg, any reported adverse events, and deaths of enrolled patients.

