**Aim 1c Procedure:**

- 1) Pre-checked, no-action default: The first nudge will be part of the CDS. We will display the CDS with certain options pre-selected. We plan to include addition of the CKD diagnosis to the problem list and addition of a patient education handout to the after-visit summary.
- 2) Pledge email to obtain commitment from PCPs to follow the CDS recommendations: As a starting point, we need to ensure that PCPs are aware of the clinical practice guidelines. At the beginning of the study, we will send an advertisement email to all PCPs in the network. In addition, as part of the intervention, we will ask PCPs to commit to following the recommendations presented to them in the BPA, or writing their rationale in the CDS if they choose not to. The PI will send an email via REDCap to intervention PCPs giving a brief overview of the CDS content. By clicking a link in the email, the intervention PCP will come to a REDCap survey asking them to type their name to pledge to consider the CDS recommendations provided in our BPAs. The control PCPs will receive a similar email without the specific details about our study and without the REDCap link.

Behavioral Science Methods Review Committee: Though the research team does include co-investigators with expertise in behavioral science methods, we have decided to convene an advisory group consisting of three experts in behavioral science as applied in interventions for both PCPs and patients. We have chosen the members of this committee based upon their familiarity with chronic disease management interventions and EHR-based interventions. We have limited the group to three members because we plan to meet on a monthly basis during the first two years of the study. This group will give advice to the research team on elements of Aim 1 and the roll-out of the clinical trial.

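### Clinical adverse events and deaths have no defined ascertainment in either arm, and relying on reports when only intervention PCPs see the alert risks differential capture

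*Combined protocol and SAP*

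**What the plan says.** Section VII names two harms that the intervention could cause: "there is a risk of overtreatment of hypertension which may cause hypotension or an acute decrease in kidney function".

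Section IX sets out the monitoring. The DSMB meets once a year. At that meeting "the board will review any cases where systolic blood pressure was found to be below 110 mmHg", along with "any reported adverse events, and deaths of enrolled patients". Between meetings, "The PI and co-investigators will review enrollment, adverse events and any recent literature that may be relevant to the research on a quarterly basis", and minutes go to the DSMB.

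The arms differ in what the PCP is told. Under the Aim 1 and 1a procedures (section V), the alert (BPA) is implemented in "silent mode” for the control arm"; the study team finds control patients as they present, using the same eligibility rules. What that mode means is spelled out only for the pre-trial validation step, under implementation in Epic: "it will record when it would fire, but it will not be displayed to the user". Under Aim 1c, intervention PCPs are asked to pledge to consider the recommendations, whereas "The control PCPs will receive a similar email without the specific details about our study".

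Table 1 in section VI applies to both arms. It has five monthly harm-type rows: mean SBP below 110, creatinine above 2.0, potassium above 5.2, potassium below 3.6, and new allergy entries attributed to adverse drug events. It also has eGFR at 6, 12 and 18 months.

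**The concern.** An adverse event that enters the safety data only when someone reports it depends on that person knowing that the patient is in a trial and that the event is of interest. In this open design, that knowledge differs by arm at the PCP level. An intervention PCP has seen an alert for the patient and has been told about the study. A control PCP has seen no alert, has an email without the specifics, and is not said to learn which patients are enrolled.

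If reports are the source for events such as syncope, falls, acute kidney injury or admission, the two arms' counts are not comparable. An excess of reports in the intervention arm could be pure reporting, and a real excess could be dismissed as reporting. The DSMB would have no planned way to tell the two apart for this class of event.

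**Working it through.** The documents state no adverse-event rate, reporting rate or safety sample size, so there is no figure to reproduce. The check compares sections and adds one algebraic step.

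**1. How each DSMB item in section IX is captured**

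- SBP below 110: a measured value, not limited to one arm, and needing no report.
- Adverse events: reviewed if reported. No definition, reporter, form or route is given.
- Deaths: listed separately from reported events, with no source stated.

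One of the three items is openly report-dependent, and one has an unknown source.

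**2. What Table 1 adds**

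- All five monthly harm-type rows are blood pressure, laboratory or allergy-list entries. None is a clinical event (syncope, fall, acute kidney injury, ED visit, admission) and none is death.
- For the kidney harm named in section VII, creatinine above 2.0 is a fixed level, not a change. Sections III and V admit patients with eGFR as low as 16, so some can exceed 2.0 at entry. An acute rise that stays below 2.0 is not counted. eGFR every 6 months is not designed to catch an acute fall.
- Section IX's list for the DSMB meeting does not name the creatinine, potassium or allergy rows.

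**3. Any other both-arm search**

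Section IV provides for monthly recording and review of clinical outcomes but defines no clinical event beyond the Table 1 rows. No section describes a search of admissions, ED visits, diagnoses or death records.

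**4. What differential reporting does to the comparison**

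Let each arm have n patients, let the true event risk be p in both arms, and let the reporting probabilities be r_I (intervention) and r_C (control).

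- Expected reported events: n × p × r_I and n × p × r_C.
- Reported ratio: r_I / r_C. Both n and p cancel.
- Intervention share of reports: r_I / (r_I + r_C).

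The documents give neither probability. Assuming r_I = 0.6 and varying r_C:

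| r_C (assumed) | Reported ratio | Intervention share |
|---|---|---|
| 0.6 | 0.6/0.6 = 1.0 | 0.6/1.2 = 50% |
| 0.4 | 0.6/0.4 = 1.5 | 0.6/1.0 = 60% |
| 0.3 | 0.6/0.3 = 2.0 | 0.6/0.9 = 67% |
| 0.2 | 0.6/0.2 = 3.0 | 0.6/0.8 = 75% |

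If the true risks differ by a ratio RR, the reported ratio is RR × r_I / r_C. A reported ratio of 3.0 then fits RR = 3 with equal reporting, or RR = 1 with threefold differential reporting. Reported counts alone cannot separate these.

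**The case against.** A reader might infer that harm data will come mainly from one arm, or that the trial cannot say whether the intervention causes the harms it names. The documents do not support either reading. Table 1 sets five harm-type measures monthly in both arms. The DSMB's low-SBP item needs no PCP report. Both harms named in section VII have at least a proxy: SBP below 110 for hypotension, and creatinine and eGFR for kidney function. Syncope, falls and ED care are clinical consequences that this review adds; the protocol does not name them.

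A reader might also treat the feedback button and the pledge as intervention-only safety routes. Table 2 does count "Proportion of patients with feedback button clicked" for the intervention arm alone, but as a usage measure, and the pledge concerns the recommendations. Neither is described as adverse-event reporting. Nor does any section name PCPs as the reporters. The investigators review adverse events quarterly and know who the control patients are, so they could search both arms alike. Deaths may well be captured evenly. The DSMB list is not said to be exhaustive, and it also receives the quarterly minutes.

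All of this stands, and it confines the point to reported clinical events and to the unstated source of deaths. It does not remove it. An even search by the investigators would be a good answer, but none is written down. With no named reporter, nothing prevents the default: reports from clinicians who happen to know about the study, who are more likely to be in the intervention arm.

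**Conclusion.** The point holds as a gap in specification that carries a risk of bias. Clinical adverse events reach the DSMB as reports, without a definition, reporter or route, and deaths have no stated source. Because the alert is visible to intervention PCPs and silent for control PCPs, capture can differ by arm. Differential capture is a possibility that the plan leaves open; the documents do not show that it will occur.

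Its size is unknown. The 1.0 to 3.0 range rests wholly on assumed reporting probabilities and on equal true risk and equal arm sizes; it shows how the bias works and is not a forecast. The Table 1 harm rows are not exposed to this reporting route (whether laboratory tests are ordered equally often in both arms is a separate question). They do not fill the gap, since they include no clinical event or death and the fixed creatinine cut-off is a weak marker of an acute decline. The primary blood pressure comparison is unaffected. This is a cheap improvement that should be made.

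**What to change.** In section IX, make the comparative source of clinical harm data a single EHR query, run identically in both arms from each patient's enrolment date over the same window. It should cover:

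- ED visits and admissions coded for hypotension, syncope or fall, acute kidney injury, and hyperkalaemia;
- death from any cause, with the source stated.

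Add these as rows in Table 1. Give them to the DSMB by arm, together with the existing Table 1 harm measures (SBP, creatinine, potassium, allergy). Keep spontaneous reports as a separate listing, labelled as not comparable between arms, and state who may file one and how.

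The cost is a set of code lists and a few lines in section IX and Table 1. The trial already identifies control patients by the same rule as intervention patients and already plans monthly measures in both arms, so the query extends existing work. The downside is that events treated outside the network will be missed. That loss should be similar in both arms, so it lowers the counts without favouring either; this is an assumption and should be stated as one.
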